4.1.4 Chi-squared test

The chi-square test will be used to assess the difference in proportion of responders. The difference between active treatment groups versus placebo will be presented with the two-sided 80% confidence intervals and the one-sided p-values.

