5.1 Inclusion Criteria

Participants are eligible to be included in the study only if all of the following criteria apply:

If any criterion cannot be fully assessed at a particular visit (eg, due to awaiting information from the participant's usual physician at SV1 or laboratory results not yet available at SV2), the criterion must be fully assessed prior to randomisation:

Age

- 1 Participant must be 18 to < 65 years of age inclusive, at the time of signing the ICF.

Type of Participant and Disease Characteristics

- 2 Documented physician-diagnosed asthma of early onset, defined as development of asthma before the age of 25 years. Asthma should be diagnosed > 12 months prior to SV1. Acceptable documentation includes any of the following:
 - (a) Contemporaneous clinical notes, dated > 12 months prior to SV1 **and** when participants were aged < 25 years, showing a diagnosis of asthma.
 - (b) Contemporaneous clinical notes or pharmacy records, dated > 12 months prior to SV1 **and** when participants were aged < 25 years, showing on-going treatment for asthma (note: the indication of asthma must be documented).
 - (c) Investigator documentation based on communication with the physician who treats the participant's asthma.
- 3 Treated with medium-to-high dose ICS defined as total daily dose of > 250 µg fluticasone dry powder or equivalent (see [Appendix F](#) for equivalent ICS doses), for at least 12 months prior to SV1 and on a stable dose for ≥ 3 months prior to SV1.
- 4 Stable LABA therapy for ≥ 3 months prior to SV1 (this may be as a fixed-dose combination product, or a separate inhaler).
 - Treatment with additional asthma controller therapies eg, LAMA, LTRA, theophylline (≥ 1 month at a stable dose) prior to SV1 is allowed. Individuals on theophylline must have normal blood levels documented in the 3 months prior to SV1. Treatment with oral corticosteroids is allowed if dose has been stable for ≥ 3 months.
- 5 An ACQ-6 score ≥ 1.5 at SV1, SV2, and SV4 (randomisation).
- 6 Morning pre-BD FEV₁ < 85% predicted normal at SV1.
- 7 ≥ 70% adherence (days) to eDiary completion both between SV1 and SV2 **and** in the 14 days preceding SV4.
 - An adherent day requires completion of evening and subsequent morning diary between SV1 (evening assessment) and SV2 (morning assessment).
- 8 ≥ 70% adherence to background medication as assessed by eDiary entries both between SV1 and SV2 **and** in the 14 days preceding SV4.

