3.4.3 Asthma control questionnaire-6 (ACQ-6)

The questionnaire will be completed using the eDiary in accordance with the SoA of the CSP.

In the ACQ-6, participants are asked to recall how their asthma has been during the previous week by responding to one BD use question and 5 symptom questions. Questions are weighted equally and scored from 0 (totally controlled) to 6 (severely uncontrolled). The mean ACQ-6 score is the mean of the responses. If response to any of the questions is missing, the ACQ-6 score will be missing. Mean scores of ≤ 0.75 indicate well-controlled asthma, scores between >0.75 and <1.5 indicate partly controlled asthma, and scores ≥ 1.5 indicate not well-controlled asthma (Juniper et al 2006). Individual changes of at least 0.5 are considered clinically meaningful.

The key outcome variable for the ACQ-6 will be the change in mean score from baseline to Week 16. The change in mean score from baseline to each of the post-randomisation assessments will also be derived (see Section 3.1.3).

Other variables based on ACQ-6 to report include:

- Proportion of participants with a decrease in ACQ-6 score of ≥ 0.5 from baseline to Week 16 (Yes=1/No=0):
 - Yes: change from baseline ACQ-6 score to ACQ-6 score at Week 16: ≤ -0.5 .
 - No: change from baseline ACQ-6 score to ACQ-6 score at Week 16: > -0.5 .
- Proportion of participants achieving ACQ-6 well controlled status (Yes=1/No=0):
 - Yes: ACQ-6 score at Week 16 ≤ 0.75 .
 - No: ACQ-6 score at Week 16 > 0.75 .

Participants with missing or non-evaluable ACQ-6 score will be considered as not achieving ACQ-6 response.

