4.1.2 Repeated measures mixed effects analysis of covariance model (MMRM)

The repeated measures mixed effects analysis of covariance model (MMRM) will be used to fit change from baseline for continuous endpoints at each visit, for the ITT population. The model will include all available data from all visits up to and including the target visit, irrespective of whether the participant discontinued study intervention or received rescue therapy. No imputation will be made for missing data, as a repeated measures model is being applied. The model will include fixed effects for baseline, background medication use, geographic region, baseline ICS total daily dose, visit, treatment and the baseline by visit and treatment by visit interactions. Visits within subject are considered as repeated measurements. An unstructured covariance matrix will be used to describe the correlations between observations on a participant between visits. The denominator degrees of freedom will be calculated using the Kenward-Rogers method. In the event that the model with unstructured covariance matrix fails to converge, an autoregressive (1) covariance matrix will be used instead. If also the autoregressive (1) does not converge, a compound symmetry covariance matrix will be used. If the model still does not converge, the baseline by visit effect will be deleted from the model. Estimates of the least square mean change from baseline in endpoint variable for each treatment, and the difference between them, together with two-sided 80% confidence interval, will be obtained from the model for each visit. The significance of the treatment effect will be tested at a 10% one-sided level of significance as described in Section 4.1.1.

The reportable results from the model will be:

- The least-square means (LSMeans) change from baseline at certain visit and their standard errors for each group
- The difference in change from baseline at certain visit between active treatments groups and placebo (LSMeans difference) together with its two-sided 80% confidence interval (CI)
- The one-sided p-value for the difference in change from baseline at certain visit between active treatment groups and placebo

If the dependent variable is considered to be normally distributed, the variable fitted in the model will be the change from baseline; the MMRM and the reportable results will be those described above.

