4.2.5.2 Analysis of ACQ-6

Change from baseline to Week 16 in ACQ-6 will be analysed using MMRM (see Section 4.1.2). LS Mean change from baseline and two-sided 80% CI through Week 24 in ACQ-6 score will be presented in figures.

Observed values and absolute change from baseline through Week 16 will be summarised by treatment group using the ITT population.

As a part of exploratory analysis change from baseline through Week 24 in ACQ-6 will also be analysed.

Number and proportion of participants with a decrease in ACQ-6 score of ≥ 0.5 from baseline to Week 16 and number and proportion of participants achieving ACQ-6 well controlled status at Week 16 (as defined in Section 3.4.3) will be summarised and analysed using chi-squared test as described in Section 4.1.4 for the ITT population.

A listing including results from each of the questions and the ACQ-6 score will be produced for the ITT population.

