14.2 ACQ		
Table 14.2.3.1	ACQ-6 score by visit, summary statistics	ITT population
Table 14.2.3.2	Change from baseline to Week 16 in ACQ-6 score treatment comparisons, MMRM	ITT population
Figure 14.2.3	Change from baseline through Week 16 in ACQ-6 score, LSMeans (80% CI)	ITT population
Table 14.2.3.3	Change from baseline through Week 24 in ACQ-6 score treatment comparisons, MMRM	ITT population

Table 14.2.3.4	Proportion of subjects achieving a decrease in ACQ-6 score of ≥ 0.5 from baseline to Week 16	ITT population
Table 14.2.3.5	Proportion of subjects achieving a decrease in ACQ-6 score of ≥ 0.5 from baseline to Week 16 treatment comparisons chi-squared test	ITT population
Table 14.2.3.6	Proportion of subjects achieving ACQ-6 well controlled status at Week 16	ITT population
Table 14.2.3.7	Proportion of subjects achieving ACQ-6 well controlled status at Week 16 treatment comparisons chi-squared test	ITT population

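### ACQ-6 well-controlled status is tested without the baseline score; adjusting for it costs about 1% of variance at worst and gains precision if baseline is moderately prognostic

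*SAP*

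**What the plan says.** - **Endpoint.** SAP 3.4.3 defines a well-controlled participant as "Yes: ACQ-6 score at Week 16 ≤ 0.75". On missing scores it adds: "Participants with missing or non-evaluable ACQ-6 score will be considered as not achieving ACQ-6 response".
- **Test.** SAP 4.2.5.2 has this endpoint "summarised and analysed using chi-squared test as described in Section 4.1.4 for the ITT population". SAP 4.1.4 states: "The chi-square test will be used to assess the difference in proportion of responders". It names no covariate or stratum and reports a difference from placebo with a two-sided 80% interval and a one-sided p-value. The table title in Appendix C is "Proportion of subjects achieving ACQ-6 well controlled status at Week 16 treatment comparisons chi-squared test".
- **Entry floor.** Protocol 5.1, criterion 5, requires "An ACQ-6 score ≥ 1.5 at SV1, SV2, and SV4 (randomisation").
- **Continuous analysis of the same score.** SAP 4.2.5.2: "Change from baseline to Week 16 in ACQ-6 will be analysed using MMRM (see Section 4.1.2"). SAP 4.1.2: "The model will include fixed effects for baseline, background medication use, geographic region, baseline ICS total daily dose, visit, treatment", plus interactions.
- **Protocol.** Section 9.4.2.2 also specifies chi-squared for the PRO responder endpoints. It states the estimand as a difference in response rates but asks for an odds ratio to be reported.
- **SAP Section 6.** It says background medication, region and baseline ICS dose are added to several models, including a logistic regression. No such regression is defined in SAP 4.1 or 4.2, and baseline ACQ-6 is not among those covariates. The move from odds ratio to difference in proportions is not listed.

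**The concern.** The endpoint is a fixed Week 16 threshold, so the improvement needed varies widely with the starting score. A participant entering at 1.5 and one entering at 3.0 face very different tasks, and the test treats them alike. Randomisation is stratified only on cough sub-study participation, so chance imbalance in baseline ACQ-6 is not otherwise dealt with.

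In SAP 4.1 the MMRM, ANCOVA, negative binomial and Cox analyses are all covariate-adjusted; the responder test is the exception. What is at stake is precision on one secondary endpoint outside the two-step testing hierarchy. Validity is not in question.

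**Working it through.** **1. The plan's own figure.** The only powered endpoint is pre-BD FEV₁. With 72 per arm, a 150 mL difference, SD 420 mL and one-sided 10%:

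- SE = 420 × √(2/72) = 70 mL
- z = 150/70 − 1.2816 = 0.861, giving power 80.5%
- 216/0.95 = 227.4, rounded up to 228 randomised

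The stated design reproduces. No power is stated for the ACQ-6 responder endpoint.

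**2. Inputs.**

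- From the documents: 72 per arm, one-sided 10%, threshold 0.75, entry floor 1.5, missing counted as non-response.
- Assumed, because the documents give none of them: baseline ACQ-6 mean 2.7 and SD 0.62 (floor 1.5), Week 16 SD 0.95, response rates of 17% vs 26% or 10% vs 18%, and baseline-to-Week-16 correlation from 0 to 0.7.

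**3. Why baseline may matter.** Fall required = baseline − 0.75. From 1.5 this is 0.75; from 3.0 it is 2.25.

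**4. Unadjusted power at 17% vs 26%.**

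- Pooled rate 0.215; null SE = √(2 × 0.215 × 0.785/72) = 0.0685
- Alternative SE = √((0.17 × 0.83 + 0.26 × 0.74)/72) = 0.0681
- z = (0.09 − 1.2816 × 0.0685)/0.0681 ≈ 0.03, so power is about 51%. Simulation gives about 52%.

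**5. Adjusted analysis.** Fit logit P(response) = a + b·treatment + c·baseline. Then average over participants i:

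risk difference = mean of [expit(a + b + c·xᵢ) − expit(a + c·xᵢ)]

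The SE is influence-function based with an n − 3 correction. Each scenario used 20,000 two-arm trials. The variance ratio is unadjusted over adjusted, with Monte Carlo SE 0.001 to 0.011. Power changes are in percentage points.

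| Correlation | 0 | 0.2 | 0.3 | 0.4 | 0.5 | 0.6 | 0.7 |
|---|---|---|---|---|---|---|---|
| 17% vs 26%, none missing: ratio | 0.99 | 1.01 | 1.04 | 1.08 | 1.13 | 1.21 | 1.33 |
| power change | +0.1 | +0.6 | +1.4 | +2.0 | +3.6 | +5.4 | +8.9 |
| 17% vs 26%, 10% missing: ratio | 0.99 | 1.01 | 1.04 | 1.06 | 1.11 | 1.17 | 1.29 |
| power change | +0.0 | +0.7 | +0.9 | +1.9 | +2.8 | +4.6 | +6.4 |
| 10% vs 18%, none missing: ratio | 0.99 | 1.01 | 1.03 | 1.05 | 1.09 | 1.15 | 1.24 |
| power change | −0.5 | −0.2 | +0.3 | +0.9 | +2.5 | +4.1 | +6.4 |

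In participants per arm, 72 × (ratio − 1) for the first scenario is about 3 at correlation 0.3 (72 × 0.04), 6 at 0.4, 9 at 0.5, 15 at 0.6 and 24 at 0.7.

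**6. Type I error.** With equal rates of 17% or 10%, over all seven correlations, it was 10.0–10.8% unadjusted and 9.8–10.6% adjusted.

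**7. Sparse cells.** Near-separation with baseline only (any coefficient beyond ±10) occurred in 0% of trials at 17% vs 26% and in 0.05–0.08% at 10% vs 18%. Adding the Section 6 covariates, simulated as non-prognostic with assumed category shares (coefficient beyond ±8; 4,000 trials per scenario), raised this to 4–5% and 14–16%. At 17% vs 26% it cut the ratio to 0.96, 1.00, 1.08 and 1.24 at correlations 0, 0.3, 0.5 and 0.7.

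**8. Cross-check with a different set-up.** This used 76 per arm, rate pairs from 10/20% to 30/45%, and prognostic strength as an odds ratio per SD of baseline.

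- Not prognostic: variance cost about 0.5–1%; power change −0.8 to +0.1 points.
- OR 0.70: power change −0.3 to +0.9 points.
- OR 0.50: worth 5–9% more participants; power +0.9 to +2.5 points.
- OR 0.37: worth 9–17% more participants; power +2.2 to +4.6 points.

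The gain is on the risk-difference scale. At 20% vs 35% and OR 0.50 per SD, the SE of the log odds ratio rises from 0.376 to 0.396 on adjustment even though power increases.

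**The case against.** The case for leaving the plan alone is substantial. The chi-squared test is valid and prescribed by the protocol, and SAP 4.1.4 reports on the scale of the protocol's estimand. The endpoint is one of three ACQ-6 secondary endpoints, and the same score already has a baseline-adjusted MMRM. Every input that drives the gain is assumed. The entry floor truncates baseline, which makes low correlation plausible; at 0 to 0.3 the gain is at most about 3 participants per arm. With rarer response and low correlation, power falls by up to 0.5 points. The larger gains need correlations of 0.6–0.7, for which the documents offer no support. The remedy also gives the two ACQ-6 responder endpoints different methods, and the simulations used two arms where the trial has three.

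All of this stands as a limit on the size of the point. It does not remove the asymmetry: with baseline as the only covariate, the worst variance ratio in the tabulated scenarios is 0.99, and the gain is real from moderate correlation upwards. The MMRM answers a different question, so it does not make the responder analysis more precise.

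**Conclusion.** The point holds as a recommended improvement, with medium confidence. The unadjusted test ignores a baseline value that fixes how far each participant must improve. Adjusting costs about 1% of variance if baseline carries no information. At correlation 0.4–0.5 it is worth about 6–9 participants per arm at 17% vs 26%. Below 0.3 the gain is negligible. These figures rest on assumed rates, spreads and correlations, on two-arm comparisons, and on a model with no covariate beyond baseline ACQ-6. No gain is claimed for the two responder endpoints defined on change (ACQ-6 by 0.5, SGRQ by 4).

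**What to change.** - **SAP 4.1.4 and 4.2.5.2.** Analyse well-controlled status by logistic regression on treatment and baseline ACQ-6 only. Report the model-standardised risk difference against placebo with two-sided 80% interval and one-sided p-value. Name the variance method and the population standardised over.
- **Keep** missing as non-response, and keep chi-squared as a sensitivity analysis for this endpoint. Leave the other two responder endpoints on chi-squared as planned.
- **Add no further covariates**, or use a Firth penalty if they are added.
- **SAP Section 6.** Make the logistic regression entry match 4.1.4, and list the change from odds ratio to difference in proportions.
- **Appendix C.** Amend the one table title.

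The cost is this wording plus one model with a standardisation step; no new data are needed. The residual risk is sparse cells if response is rare, which was very small with baseline as the only covariate.

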4.1.5 Negative binomial regression

Negative binomial regression will be used for the analysis of event rates. In this study the response variable in the model will be the number of asthma CompEx events, the number of asthma exacerbations, or the number of hospitalised asthma exacerbations experienced by a participant. The model will include treatment group, background medication, geographic region and baseline ICS total daily dose as covariates. The logarithm of the participant's corresponding follow-up time will be used as an offset variable in the model to adjust for participants having different exposure times during which the events occur.

The standard parameterization approach (NB2) of the negative binomial model will be applied using PROC GENMOD (SAS procedure).

The estimated annualised event rate in each group, the estimated treatment effect (ie, the rate ratio of each treatment group versus placebo), corresponding two-sided 80% CI, and one-sided p-value for the rate ratio will be presented. The estimate of the negative binomial overdispersion parameter will also be reported.

4.1.6 Cox proportional hazards

Time to first asthma CompEx event/ first asthma exacerbation data will be analysed using Cox proportional hazard model including treatment group, background medication, geographic region and baseline ICS total daily dose as covariates. Results of the analysis will be summarised as hazard ratios, two-sided 80% confidence intervals and one-sided p-values. Time to first asthma CompEx event/ asthma exacerbation will be displayed graphically using a Kaplan-Meier plot.

4.2 Analysis of variables

4.2.1 Disposition of subjects

Subject dispositions (number and percentage of participants enrolled, participants randomised, participants not randomised (incl. reasons), participants who received at least one dose of study IP, participants who did not receive treatment, participants who completed the treatment, participants who did not complete treatment (incl. reasons), participants who completed the study and participants withdrawn from study (incl. reasons)) will be presented in a summary table for each treatment group and overall. A listing including all standardized disposition terms will be also provided for all discontinued subjects. The table will be based

on 'All Subjects' population and repeated for the ITT population. The listing will be based on the ITT population.

The number of participants belonging to each analysis population will be presented in a summary table by treatment group and overall. Listing of all participants excluded from any analysis set will be also provided. The listing will include reason for exclusion from respective.

The number and percentage of subject recruitment by region and country will be presented for the ITT population.

The number and percentage of participants with one or more disruption due to COVID-19 pandemic will be presented by treatment group and overall. A listing of all participants affected by the COVID-19 related study disruption, and a description of how the individual's participation was altered, will be produced. COVID-19 related study disruptions can be:

- Visit related (if visit is impacted by global/country situation, then contact mode will be specified);
- Study drug related (if study drug administration or location was impacted by global/country situation; who performed a study drug administration);
- Concomitant medication related (if when treatment was stopped due to any global/country related situations ie: epidemic/pandemic, healthcare crisis etc.);
- Withdrawal from study (if primary reason for ending study is related to global/country situation).

Participants with reported issues in the clinical trial management system due to COVID-19 will be listed.

Randomisation scheme and codes as well as subjects receiving the various batch of investigational product will be listed.

Number and percent of participants remaining on treatment, discontinued treatment but still in study, and participants withdrawn from the study at each scheduled visit will be summarised. Participants completing the study will be listed.

Number and percentage of participants in sub-study will be summarised for the ITT population.

4.2.2 Important protocol deviations

The number and percentage of participants with at least one IPD, including COVID-19 related IPD, will be summarised based on the categories specified in the Protocol Deviation Plan (PDP), for each treatment group and overall.

All IPDs will be also listed based on the ITT population. All issues reported due to COVID-19 pandemic, regardless of whether the type of issue is considered a protocol deviation or not, will be listed separately (see Section 4.2.1).

4.2.3 Baseline assessments and other subject-specific characteristics

4.2.3.1 Demographics and subject-specific characteristics

All demographic and subject-specific characteristics reported in section 3.2.1.1 will be presented in summary tables for each treatment group and overall; age, height, weight and BMI will be summarised descriptively; all the other demographic and subject-specific characteristics will be summarised as categorical variables with the number and percentages of participants by categories. Only the baseline measurement for height, weight and BMI will be considered.

All demographic and subject-specific characteristics will be also provided in listings. The tables and the listings will be based on the ITT population.

4.2.3.2 Medical history

Medical history as described in section 3.2.1.2 will be presented in summary tables as number and percentages of participants by System Organ Class (SOC) and Preferred Term (PT) for each treatment group and overall. Participants with multiple events in the same SOC/PT will be counted only once in that SOC/PT. Participants with events in more than one SOC/PT will be counted once in each of those SOC/PT. Tables will be sorted alphabetically by SOC and PT. The tables will be based on the ITT population.

4.2.3.3 Prior and concomitant medication

The number and percentage of participants receiving prior or concomitant medication, excluding ICS and ICS containing medications, (by ATC4 classification system codes and generic name) will be presented by treatment in separate tables for the ITT population.

A separate table will be presented for participants who take disallowed concomitant medications, excluding ICS and ICS containing medications. Percentages will be calculated relative to the number of participants in the ITT population.

All medications will also be listed by subject for the ITT population.

